2.6 Pre-Treatment Procedures

If the subject is of childbearing potential (i.e. females not post-menopausal or not surgically sterile), they will be asked if they are pregnant, the date of their last menstrual cycle, and perform a urine pregnancy test. A urine pregnancy test will be performed on all women of childbearing potential prior to each treatment. A urine pregnancy test may also be conducted at the Investigator's discretion at any time during the study. If a urine pregnancy test is conducted, then a negative result must be obtained within 24 hours prior to the treatment.

Urine Pregnancy Test Procedure:

- A urine sample is tested mid-stream or by cup sample with an indicator stick.
- Negative results are indicated on the indicator stick.

- The area to be treated will be identified and may be marked with a surgical marker.
- Caliper measurements of both flanks will be taken prior to the first treatment and prior to treatment 4 and may be taken prior to other treatment visits as well.
- Photographs will be taken prior to the first treatment and prior to treatment 4 and may be taken prior to other treatment visits as well.
- The treatment area and the neutral pad area may be cleansed with water and soap and/or an alcohol wipe.
- The neutral pad will be placed on the back in an area determined by the Investigator to maintain standard energy settings and to require less power from the device during the treatment.

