2.9 Follow Up

- Subjects will receive a phone call 1 week (1-10 days) after each treatment to record side effects.
- The study subjects are required to return to investigator site for a follow up evaluation at 6 weeks and 12 weeks post last treatment.
- Photographs and caliper measurements of both flanks will be taken at all follow up visits.
- Subject's weight will be recorded at all follow up visits.
- Subject questionnaires will be performed at all follow up visits.
- Adverse events will be documented at all follow up visits.
- Some subjects may have an incomplete response or no response by the end of the study. After the subject has completed their participation in the study, a treatment on the untreated flank using the TempSure® Firm may be performed upon the subject's request at no cost.

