2.13 Evaluation Methods

Photographs:

Photographs will be taken prior to treatment 1, prior to treatment 4 (post treatment 3), and at all follow-up visits and may be taken at each treatment and will be used to assess safety and efficacy of treatment.

Blinded Evaluation:

Three blinded independent reviewers will perform a photographic evaluation in which they will be asked to identify pre-treatment images when compared to post treatment images. The reviewers will be Board Certified Dermatologists and be chosen based on availability and have relevant clinical experience. They will attend a training session prior to grading.

Caliper:

Caliper measurements on both flanks will be taken prior to treatment 1, prior to treatment 4 (post treatment 3), and at all follow-up visits and may be taken at each treatment.

Caliper Procedure:

The caliper device is a hand-held instrument like a compass, that is used to measure the distance between two opposite sides. The clinician will measure the flank by using a diagonal fold directly above the iliac crest. The patient's skinfold will be pinched approximately 1 cm from the measurement spot and the caliper will be placed on the skinfold. The caliper provides a measurement (millimeters) of the thickness of skin and fatty tissue. Three readings should be taken and an average of all three sites should be calculated and documented.

Treatment Discomfort/Pain Evaluation:

Subjects will be asked to report the general level of treatment discomfort on a scale of 0 (none) to 10 (maximum intolerable pain) using the universal pain assessment tool (Appendix B)

Subject Questionnaire:

The subject will be asked their level of satisfaction using a 6-point Likert scale that ranges from "extremely satisfied" to "extremely unsatisfied."

Subject Satisfaction	
Rating	Description
6	Extremely Satisfied
5	Satisfied
4	Slightly Satisfied
3	Slightly Unsatisfied
2	Dissatisfied
1	Extremely Unsatisfied

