2.14 Adverse Event Recording

All data captured must be supported by the Investigator's timely assessment and documentation of the adverse event in the case report forms or source documents. All documented adverse events will be reviewed by the Sponsor or designee to determine whether the adverse event meets regulatory reporting requirements and to ensure timely adverse event reporting to meet local and global regulatory requirements.

Adverse Events Pertaining to the TempSure Device:

Mild discomfort during treatment may be experienced by the subject. Typically, the discomfort is temporary and localized within the treatment area. Mild edema (swelling) and erythema (redness) may occur. Initial studies indicate that these side effects typically resolve within 2 to 24 hours.

Other anticipated side effects may include; pain, skin burns, bleeding, scarring, crusting, bruising, infection, itching,

prolonged edema (swelling) and erythema (redness), hardness, and nodules. Loss of hair pigment may also occur within and adjacent to the treatment area.

Adverse Events Pertaining to Gel:

The gel is a water-based gel that may be placed on the skin during the TempSure® Firm treatment. No known adverse events are documented. However, an allergic reaction is always possible when placing a topical gel onto the skin. Allergic reaction may include a mild reaction such as skin redness, irritation, or hives.

Adverse Events Pertaining to Neutral Pad:

Mild heat or hot spots may be felt during treatment by the subject. If the subject reports heat at the pad site, evaluate the site, check for epidermal injury. Skins burns may occur if subject does not report if the pad becomes too hot.

Adverse Events Pertaining to the Surgical Marker:

Using surgical marker has minimal risks and may produce effects on the body such as redness or a rash. Markings may remain visible for a few days or may be removed with alcohol.

Other Cautions:

Incomplete response or no response may occur since some subjects may not respond to treatment. After the subject has completed their participation in the study, a treatment on the untreated flank using the TempSure® Firm may be performed upon the subject's request at no cost.

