2.15.5 Analysis of Efficacy Variables

The primary efficacy variable is blinded evaluation of photographs from baseline to Visit 8 (12-week follow up) with respect to fat reduction. Baseline is defined as the last assessment prior to the first treatment. Photos will be graded and the total and percentage of photos correctly identified will be compiled and analyzed. Correct identification percentages will be calculated for each individual reviewer as well as a summary for all three reviewers. Clinical success of grading will be declared if 80% independent reviewers achieve 80% correct identification of the photos.

The secondary efficacy variables are caliper measurements of fat thickness and subject satisfaction rates. As with the primary efficacy variable the assessment at Visit 8 (12-week follow up) will be primary. The analysis and summaries for caliper measurements will include a pairwise treatment group comparison as well as repeated measure ANOVA analysis. Statistical significance with respect to both the treatment and control group comparisons as well as repeated measures of the treatment group will be declared if the two-sided p-value is <0.05 . For each treatment group and timepoint of the caliper measurements a statistical summary will be completed. The summary will include sample size mean, median, standard deviation, minimum, and maximum. The statistical significance of the mean change from baseline to follow-up for each group as well between the treatment and control will be determined using a paired t-test. Subject satisfaction will be analyzed with standard descriptive statistics which include total number of responses in each category as well as the percentage of responses for each category. Clinical success of subject satisfaction surveys will be declared if at least 80% of subjects respond they are satisfied.

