13.0 PHOTOGRAPHY

Standardized and 3D photographs will be taken of the treatment area. Photographs will be taken with an appropriate high-resolution digital camera. Camera settings (lighting, distance, background, polarization, etc.) will be reproduced at

each visit, so that photographs are suitable for comparison. Photographs will be taken of the treatment area for study purposes. If the subject does not wish to have their photographs taken, they cannot be in the study.

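### Section 2.6 lets sites mark the treatment area before the baseline photographs, so ink can show reviewers which image is pre-treatment whether or not fat changed

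*Combined protocol and SAP*

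**What the plan says.** Section 2.6 (Pre-Treatment Procedures) gives an unnumbered list. Four of its items matter here, in this order:

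- Marking: "The area to be treated will be identified and may be marked with a surgical marker".
- Caliper measurement of both flanks.
- Photographs: "Photographs will be taken prior to the first treatment and prior to treatment 4 and may be taken prior to other treatment visits as well".
- Cleansing: "The treatment area and the neutral pad area may be cleansed with water and soap and/or an alcohol wipe".

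Section 2.14, on the surgical marker, says: "Markings may remain visible for a few days or may be removed with alcohol".

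For follow-up, Section 2.9 says: "Photographs and caliper measurements of both flanks will be taken at all follow up visits". Neither Section 2.9 nor the visit schedule in 2.12 lists marking at the 6-week or 12-week visit.

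On photographic conditions, Section 13.0 says: "Camera settings (lighting, distance, background, polarization, etc.) will be reproduced at" each visit. It does not mention ink or other markings.

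In Section 2.13 the blinded reviewers' task is that "they will be asked to identify pre-treatment images when compared to post treatment images". Section 2.15.5 says "Baseline is defined as the last assessment prior to the first treatment". It declares success on grading when 80% of the reviewers each achieve 80% correct. Section 2.15.2 takes 50% correct as the result with no effect.

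No section tells sites to photograph before marking or to remove ink before photographs. None calls for images to be checked, cropped or masked for ink before grading.

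**The concern.** The endpoint asks which of two images came first. Any feature that is systematically present on one side of the pair answers that question without reference to fat. Surgical ink is such a feature: the plan's own procedure can create it, and only on the baseline side, because ink that lasts a few days will be gone 12 weeks after the last treatment. The cue works in one direction, towards a correct answer.

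Keeping reviewers blind to study information does not help when the cue is in the image. The success rule is a fixed 80% threshold, so a score raised by ink would pass without any sign that it was raised. At stake is whether a positive photographic result can be attributed to a change in the flank.

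**Working it through.** **1. The plan's own figure.** Section 2.15.2 compares 50% (SD 50%) with 80% (SD 20%), two-sided 0.05, power 95%, two-sample t-test.

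- Normal approximation: n = (0.5² + 0.2²) × (1.960 + 1.645)² / 0.3² = 41.9 per group.
- Noncentral t with 2n − 2 degrees of freedom: power 0.9461 at n = 42 and 0.9506 at n = 43.

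The stated 43 is reproduced. The sample-size arithmetic is not in question here; the 50% no-effect rate that goes into it is.

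**2. What the success rule requires.** With three reviewers, 80% of reviewers is 0.8 × 3 = 2.4, so all three must pass (two of three is only 67%). With 68 gradable pairs, each reviewer needs 0.8 × 68 = 54.4, so 55 correct.

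**3. Expected score with ink.** Let m be the share of pairs with ink visible at baseline only. The documents give no value for m, so it is an assumption shown over a range. Assume inked pairs are always identified and uninked pairs are identified with probability p.

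Expected correct rate = m + (1 − m)p.

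With no fat change (p = 0.5) this is 0.5 + 0.5m. It reaches 80% at m = (0.80 − 0.50)/0.50 = 60%.

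**4. Probability of passing.** Let the number of inked pairs be K ~ Bin(68, m), shared by all reviewers. Given K, each reviewer scores K + Bin(68 − K, p) with independent guesses. The probability that one reviewer reaches 55, given K, is cubed for the all-three rule and then averaged over K.

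No fat change (p = 0.5), N = 68:

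| m | One reviewer ≥ 80% | All three ≥ 80% |
|---|---|---|
| 0 | 1.4 × 10⁻⁷ | about 0 |
| 0.4 | 3.0% | 0.1% |
| 0.5 | 16% | 2% |
| 0.6 | 50% | 22% |
| 0.7 | 87% | 71% |
| 0.8 | 99% | 98% |

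Uninked pairs identified 70% of the time (p = 0.7), N = 68: at m = 0.4 the expected rate is 0.4 + 0.6 × 0.7 = 82%. The all-three probability rises from about 0% at m = 0 to 33% at m = 0.4.

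**5. Sensitivity.**

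- Fixing the number of inked pairs instead of sampling it leaves the 60% break-even unchanged. The all-three probability becomes 12.5% at 41 of 68 inked and 84% at 48 of 68.
- With 43 gradable pairs (35 correct needed) and K sampled, the all-three probability at m = 0.7 is 62%.
- Pooling the three reviewers' readings (164 of 204 needed) is an easier test: 0.5% at m = 0.4, 49% at 0.6 and 92% at 0.7. The main figures use the all-three rule because Section 2.15.5 applies the threshold reviewer by reviewer.

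**The case against.** The strongest reply is that the plan permits this cue but does not require it. Marking is optional. The bullets in 2.6 are not declared a working sequence, and read literally the order sits awkwardly, since an alcohol wipe after marking could remove the guide before treatment. A site may well photograph first. This stands: the documents do not support an inference that baseline images will be inked, or that m is anywhere near 60%. With no fat change, ink in a minority of pairs would rarely carry the criterion.

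The graded image also need not be a treatment-day image. Section 2.12 schedules photographs at the screening visit, which may be on a separate day, and the baseline definition in 2.15.5 does not name the treatment day. This stands too, although that visit is itself titled as including pre-treatment procedures, so the 2.6 list can apply there.

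A reader might further infer that the trial could succeed with an ineffective device. The documents do not support that. Section 2.15.1 also requires significant caliper improvement against the control flank, at least 80% satisfaction and an acceptable side-effect profile, and ink in a photograph supplies none of these.

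Finally, the operator manual, the clinical reference guide or site training might cover marking and image preparation. They are not in the documents reviewed, so this cannot be settled. The protocol text itself contains no safeguard.

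**Conclusion.** The concern holds as a gap in the photographic procedure. The plan allows, and its listed order suggests, marking before the baseline photographs, and nothing keeps ink out of the graded images. For any pair so affected, the 50% no-effect rate in Section 2.15.2 does not apply.

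The size depends on m, which is unknown. With a wholly ineffective device the effect is negligible at m = 0.4 and serious from about m = 0.6. With a modest true effect, m = 0.4 already matters. These figures assume that every inked pair is identified, that reviewers guess independently on the rest, and that all 68 enrolled subjects yield a gradable pair, although Section 2.15.2 includes dropout in the 68.

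The point concerns the photographic primary criterion alone. It is a cheap improvement that should be made; it is not evidence that the result will be biased.

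**What to change.** - **Section 2.6:** place the photographs before marking, and state that all photographs used for efficacy grading are taken on unmarked skin with any residual ink removed. Apply the same condition in Sections 2.9 and 13.0.
- **Before grading:** have existing staff outside the review panel check the images for ink.
- **Pairs already affected:** crop or mask the same region in both images, provided the contour being graded stays visible. Report the correct-identification rate with and without these pairs.
- **Earlier unmarked images:** use them only in a sensitivity analysis. Making one the primary baseline would conflict with the last-assessment definition in Section 2.15.5 unless that definition is amended.

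The cost is one reordered bullet, a sentence in three sections and an image check. No visits, reviewers or subjects are added. The downside is slightly fewer gradable pairs or a slightly lower correct rate.

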2.7 Treatment Procedures

- The Investigator will use the device as described in the TempSure Operator's Manual and Clinical Reference Guide.
- Gel will be applied to the treatment area.
- The TempSure® Firm handpiece (25mm, 30mm, 60mm) to be used and the limits of the area to be treated will be determined by the Investigator and will be used in accordance with the Tempsure Clinical Reference Guide.
- The handpiece will be placed in contact with the skin.
- The entire defined treatment area will then be treated by delivering energy to the skin.
- Parameters may be adjusted throughout the treatment to increase subject comfort.
- Subjects will be asked to report the general level of treatment discomfort/pain on a scale of 0 (none) to 10 (maximum intolerable pain).

- Temperature will be continuously monitored and recorded during treatment.
- Photographs may be taken at any time during treatment to document treatment area and any adverse events, if applicable.
- Subjects may receive up to 5 treatments every 1-2 weeks.
- The additional treatments will follow the same procedure.
- Adverse Events will be documented at all treatment visits.

2.8 Post Treatment Procedures

- Adverse events will be documented after treatment.
- Post treatment instructions will be reviewed.
- Photographs may be taken.

2.9 Follow Up

- Subjects will receive a phone call 1 week (1-10 days) after each treatment to record side effects.
- The study subjects are required to return to investigator site for a follow up evaluation at 6 weeks and 12 weeks post last treatment.
- Photographs and caliper measurements of both flanks will be taken at all follow up visits.
- Subject's weight will be recorded at all follow up visits.
- Subject questionnaires will be performed at all follow up visits.
- Adverse events will be documented at all follow up visits.
- Some subjects may have an incomplete response or no response by the end of the study. After the subject has completed their participation in the study, a treatment on the untreated flank using the TempSure® Firm may be performed upon the subject's request at no cost.

2.10 Unscheduled Visits

An unscheduled visit may be performed at any time during the study at the subject's request or as deemed necessary by the site Investigator. The date and reason for the unscheduled visit will be recorded in the source documentation.

2.11 Replacement of Subjects

Replacement of subjects who have withdrawn or been withdrawn from the study will be allowed to be replaced with prior approval from the sponsor and/or IRB.

2.12 Schedule of Visits and Procedures

	Visit #1*	Visit #2-6	Call	Visit #7	Visit #8
Procedure	Screening and Pre-treatment Procedures	Treatment Visit(s) 1-5 (1 – 2 Weeks Apart)	Phone Call 1 Week Post Each Tx (1-10 Days)	Follow Up 6 Weeks Post Last Tx (+/- 1 Week)	Follow Up 12 Weeks Post Last Tx (+/- 1 Week)
Medical History	X				
Weight	X	X		X	X
Pregnancy Verification**	X	X			
Informed Consent	X				
Photographs***	X	X		X	X
Caliper Measurement***	X	X		X	X
Treatment		X			
Treatment Discomfort/ Pain Evaluation		X			
Subject Questionnaires		X		X	X
Adverse Events Assessment	X	X	X	X	X

*Screening and Pre-treatment Procedures may occur at the same time as the Treatment Visit #1.

**Pregnancy verification required before each treatment only for women of childbearing potential.

***Photographs, caliper measurements, and weight will be taken prior to Treatment Visit #1 and prior to treatment on Treatment Visit #4 (post treatment 3) and at the 6 week and 12 week follow up visits.

2.13 Evaluation Methods

Photographs:

Photographs will be taken prior to treatment 1, prior to treatment 4 (post treatment 3), and at all follow-up visits and may be taken at each treatment and will be used to assess safety and efficacy of treatment.

Blinded Evaluation:

Three blinded independent reviewers will perform a photographic evaluation in which they will be asked to identify pre-treatment images when compared to post treatment images. The reviewers will be Board Certified Dermatologists and be chosen based on availability and have relevant clinical experience. They will attend a training session prior to grading.

Caliper:

Caliper measurements on both flanks will be taken prior to treatment 1, prior to treatment 4 (post treatment 3), and at all follow-up visits and may be taken at each treatment.

Caliper Procedure:

The caliper device is a hand-held instrument like a compass, that is used to measure the distance between two opposite sides. The clinician will measure the flank by using a diagonal fold directly above the iliac crest. The patient's skinfold will be pinched approximately 1 cm from the measurement spot and the caliper will be placed on the skinfold. The caliper provides a measurement (millimeters) of the thickness of skin and fatty tissue. Three readings should be taken and an average of all three sites should be calculated and documented.

Treatment Discomfort/Pain Evaluation:

Subjects will be asked to report the general level of treatment discomfort on a scale of 0 (none) to 10 (maximum intolerable pain) using the universal pain assessment tool (Appendix B)

Subject Questionnaire:

The subject will be asked their level of satisfaction using a 6-point Likert scale that ranges from "extremely satisfied" to "extremely unsatisfied."

Subject Satisfaction	
Rating	Description
6	Extremely Satisfied
5	Satisfied
4	Slightly Satisfied
3	Slightly Unsatisfied
2	Dissatisfied
1	Extremely Unsatisfied

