2.0 PROTOCOL**2.1 Protocol Methodology and Analysis****Methodology:**

Subjects are to be enrolled in this clinical study if they are 18 – 55 years old. A maximum of 68 subjects will be enrolled at up to 6 study centers. Subject will attend a screening/pretreatment visit which may be performed on the same day as the treatment visit. Subjects will receive up to 5 treatments with the TempSure® Firm on one flank. The other flank will be left untreated to serve a control. Subject will be required to return for follow-up visits at 6 weeks and at 12 weeks after the subject's final treatment. All subjects will receive a phone call 1 week (1-10 days) post each treatment. An unscheduled visit or phone call may be performed at any time during the study at the subject's request or as deemed necessary by the site Investigator.

Analysis:

Upcoming generations are proving to have an interest in non-ablative aesthetic treatments and will drive demand for innovated products, procedures, and practice design.ⁱ Due to this shift in patient base, practices need to evolve to adapt to the newer generational ideologies. There have been rapid advances in RF technology over the past few years and the nonsurgical treatment using this energy source offers great promise to our aging population.ⁱⁱ Radiofrequency technology for lipolysis needs to be further investigated to optimize treatment parameters for safe and effective non-ablative aesthetic treatments.

Relevance:

Non-invasive fat reduction is a commonly sought out procedure and continues to increase in demand (+3% from 2018 to 2019)³ perhaps due to the fact that, according to the CDC, the prevalence of obesity in the U.S. was 42.4% in 2017-2018⁴. Currently, the treatments available for non-invasive lipolysis include, but not limited to, radiofrequency, cryolipolysis, laser lipolysis, HIFEM, and ultrasound. The limitations of current products on the market include different side effect profiles and modes of administration.

Testability:

The CoolSculpting device has been cleared for used for cold-assisted lipolysis(breakdown of fat) of bra fat, back fat, banana roll, submental area, thigh, abdomen, and flank, or "love handles" in individuals with a Body Mass Index

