2.15.3 Patient Populations

Interim results may be collected and reported. All data will be analyzed at the end of the study. The primary analysis will be performed by the intention-to-treat approach. Everyone who begins the treatment is part of the study whether he or she completes the study or not. Additional per-protocol analysis may also be performed on subjects who complete the entire clinical trial according to the protocol. The most appropriate method of handling missing values will be chosen based on the trial's goals, endpoints and context.

The analysis of demographic, medical history, and efficacy variables will be based on all patients who are randomized and receive at least one treatment. The analysis of safety data will be based on all patients who are randomized, receive at least one treatment, and have at least some safety data.

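### Run as a complete-case analysis of all four scheduled readings, the caliper repeated-measures ANOVA would leave out subjects who stop treatment before the treatment-4 visit but stay in follow-up

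*Combined protocol and SAP*

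**What the plan says.** **Number of treatments.** Section 2.1 says "Subjects will receive up to 5 treatments with the TempSure® Firm on one flank", and section 2.7 says "Subjects may receive up to 5 treatments every 1-2 weeks". Both give a maximum. Neither gives a minimum.

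**Caliper schedule.** Section 2.13 requires: "Caliper measurements on both flanks will be taken prior to treatment 1, prior to treatment 4 (post treatment 3), and at all follow-up visits". The third footnote to the schedule in 2.12 gives the same four time points. Section 2.6 makes readings at the remaining treatment visits optional: "prior to treatment 4 and may be taken prior to other treatment visits as well".

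**Follow-up.** Section 2.9 asks for "follow up evaluation at 6 weeks and 12 weeks post last treatment", so the follow-up visits exist however many sessions were given.

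**Analysis set and missing data.** In 2.15.3, demographic, medical history and "efficacy variables will be based on all patients who are randomized and receive at least one treatment". On missing data the same section says: "The most appropriate method of handling missing values will be chosen based on the trial's goals, endpoints and context".

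**Method.** Section 2.15.5 says: "The analysis and summaries for caliper measurements will include a pairwise treatment group comparison as well as repeated measure ANOVA analysis". It makes Visit 8 the main assessment. It uses a paired t-test for mean change from baseline and for treated versus control. It declares significance at two-sided p<0.05 both for that comparison and for repeated measures in the treatment group.

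**The concern.** The mid-course reading is tied to a treatment number that some subjects may never reach. For them the reading is absent because the visit does not take place, and nothing in the plan has been broken. The classical repeated-measures ANOVA needs every time point for each subject. Applied to all four scheduled readings, it would discard these subjects' 6-week and 12-week readings along with the one that was never due.

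Two things are at stake. The ANOVA's declaration of significance would describe only subjects measured at the treatment-4 visit, and not the efficacy set of 2.15.3. The two caliper analyses in 2.15.5 would also rest on different subjects, with no rule written in advance to say so.

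**Working it through.** **1. The plan's own figure.** Section 2.15.2 gives changes of 7.0 mm (treated) and 0.7 mm (control), SD 5.8 mm, significance level 0.05, power 95% and 14 subjects. The difference is 7.0 − 0.7 = 6.3 mm. For a two-sided paired t-test with 5.8 mm as the SD of the paired difference, power comes from the noncentral t with n − 1 degrees of freedom and noncentrality (6.3/5.8)√n.
- n = 13: 94.8%
- n = 14: 96.3%

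The stated 14 reproduces.

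**2. Readings held by a subject who stops after one to three sessions, misses the treatment-4 visit and completes follow-up.**

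| Reading | Required by 2.13 | Available |
|---|---|---|
| Before treatment 1 | yes | yes |
| Before treatment 4 | yes | no, the visit does not occur |
| 6 weeks after last treatment | yes | yes |
| 12 weeks after last treatment | yes | yes |

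**3. Which analyses keep this subject.** In a constructed data set of 68 subjects, each with two flanks and four time points, 12 had no treatment-4 reading.
- ANOVA on four time points: rejected the unbalanced data; deleting incomplete subjects left 68 − 12 = 56.
- ANOVA on baseline, 6 and 12 weeks: 68 subjects.
- Mixed model on all readings: 68 subjects, 68 × 8 − 12 × 2 = 520 readings.
- Paired t-test on change to Visit 8: 68 subjects.

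**4. Size.** The documents give no early-stop rate, so the share f is assumed, with no other missed readings. Retained subjects are 68(1 − f), rounded down. The standard error grows by 1/√(1 − f). Suppose full-course subjects have the planned 6.3 mm effect and early stoppers have effect e. The complete-case mean then exceeds the all-treated mean by 6.3 − [(1 − f)6.3 + f·e] = f(6.3 − e).

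| f | Retained | SE factor | Excess, e = 0 | e = 3.15 mm | e = 6.3 mm |
|---|---|---|---|---|---|
| 10% | 61 | 1.054 | 0.63 mm | 0.315 mm | 0 |
| 20% | 54 | 1.118 | 1.26 mm | 0.63 mm | 0 |
| 30% | 47 | 1.195 | 1.89 mm | 0.945 mm | 0 |

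For example, with f = 20% and e = 3.15 mm the all-treated mean is 0.8 × 6.3 + 0.2 × 3.15 = 5.67 mm, against 6.3 mm in complete cases. If early stoppers responded better than the others (e above 6.3 mm), the sign would reverse.

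**5. Power.** On the plan's inputs, power stays above 95% until fewer than 14 subjects remain, a loss of more than (68 − 14)/68 = 79%. If the SD of the paired difference were instead 5.8 × √2 = 8.2 mm, 25 subjects would be needed. All the retained numbers in the table exceed that too.

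**The case against.** A reader might infer that the planned ANOVA does drop early stoppers. The documents do not say so. Section 2.15.5 names neither the ANOVA time points nor complete-case deletion, and 2.15.3 leaves missing-value handling to be chosen. An ANOVA on baseline, 6 and 12 weeks would fit the text equally well and lose none of these subjects. This objection stands, and it makes the point conditional.

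A reader might also infer that the retained group must look better, because people stop for discomfort or lack of response. That is an assumption. Section 2.14 expects discomfort to be mild and temporary, and 2.7 allows settings to be adjusted for comfort. Section 3.3 puts fat clearance at weeks to months, while three sessions one to two weeks apart span only two to four weeks, so stopping that early for visible non-response is doubtful. The documents give no reasons for stopping, so the direction of bias is open.

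The affected group is also narrow. A subject measured at the treatment-4 visit who then declines treatment has the reading. Under section 12.0, subjects who withdraw from the study may be asked for a final visit but otherwise give no further data, so many would lack follow-up readings anyway. The schedule in 2.12 is laid out for five treatments, and nothing suggests that early stopping is expected.

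Finally, the Visit 8 paired comparison of treated with control flank does not use the treatment-4 reading. That comparison matches the caliper success criterion in 2.15.1, so the ANOVA is best read as supportive.

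What the objection does not remove is the gap itself. Subjects can lack the reading by design, they belong to the efficacy set, the named method in its classical form cannot use them if all four readings enter, and a method to be chosen later is not a rule.

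**Conclusion.** The point holds as a conditional risk and is minor. It bears on a supportive analysis of a secondary endpoint, and only if the ANOVA is run on complete cases at all four scheduled readings and some subjects stop before the treatment-4 visit while remaining in follow-up. The ANOVA and the Visit 8 paired t-test would then rest on different subjects.

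At assumed early-stop rates of 10% to 30% the ANOVA would keep 61 to 47 of 68 subjects. The illustrative overstatement of 0 to 1.89 mm rests on those rates, on the planned 6.3 mm effect in full-course subjects, and on early stoppers having between no effect and the full effect. It shows scale and is not a prediction. The documents support no conclusion about the actual direction or size of bias. Power is not a concern, and the Visit 8 paired comparison of the two flanks is unaffected.

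**What to change.** In 2.15.5, replace the repeated-measures ANOVA with a linear mixed model for caliper thickness, with flank, time and flank-by-time as fixed effects and correlation allowed within subject and within flank. Fit it to all available readings in the 2.15.3 efficacy set, and report the flank-by-time contrast at Visit 8. State that an absent treatment-4 reading does not remove a subject. The model assumes that readings are missing at random given the observed ones, and the text should say so.

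Report the number of treatments received descriptively only. It arises after randomisation, so comparing effects across its levels would not be a randomised comparison.

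Limiting the ANOVA to baseline, 6 and 12 weeks would also keep these subjects, but it discards the mid-course readings that exist and still drops anyone who misses one follow-up visit.

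The sections on number of treatments (2.1, 2.7) and on required readings (2.6, 2.12, 2.13) should be reconciled with this analysis text. No view is taken here on how many treatments should be given. The cost is analysis-plan wording only, with no added visits, readings or subjects.
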